### 10.3 PRESENTATION OF PD DATA

#### 10.3.1 Handling of missing data

Missing concentration data for all subjects who are administered scheduled study treatments will be considered as non-informative missing and will not be imputed. No concentration estimates will be provided for missing sample values.

For the derivation of PD parameters and presentation of individual and summary PD data, the following rules will apply:

Concentration values below the assay's lower limit of quantification (BLQ) in pre-dose samples and in samples taken before the time of the first quantifiable concentration will be treated as zero;

The sampling time of pre-dose samples relative to dosing including 1st dosing in Part 2 for each dose level will also be treated as zero;

Post-dose BLQ values after the first quantifiable time point will be set to 0.

If the actual time of sampling is missing, the planned time may be used.

Assessments done outside the sampling windows may be excluded from by-time point summary statistics; this will be determined prior to database lock.

No further imputation will be applied to any missing values.

Statistical Analysis Plan

Catalyst Biosciences, Inc. Protocol # MAA-201

Version 2.0

Syneos Health #1009647

### 10.3.2 Listing and Presentation of Individual PD Results

The actual assessment time or sampling for PD biomarkers will be listed for each subject in both parts of the study and will include the deviation in time from the protocol scheduled time, if applicable. Both actual measurements and change from baseline for each parameter will be presented. Baseline value will be defined as the last available value of PD biomarker before the 1st dose of the drug for part 1a, part 1b and part 2 separately.

Subjects with protocol deviations affecting PK may be flagged and excluded from summaries.

Individual PD actual measured and change from baseline data will be listed by subject, time point and treatment (in relevant concentration units) separately for Parts 1 and 2. For Part 2 the time from start of 1st dose level and time elapsed from dose escalation as well as actual dose used will be presented in the listing.

The PD results and change from baseline will be summarized at each time point by actual treatment. For the Part 2 of the study this summary will be grouped by actual dose level administered taking into account dose escalation history.

Individual PD parameters for Parts 1a and 1b will be listed for the PD population and will be summarized by treatment. Individual PD parameters for Part 2 will be listed separately for each dose level.

#### The following figures will be produced for PD results:

Individual PD data-time profiles for actual measurement and change from baseline results will be presented for Parts 1a, 1b and 2 separately with all subjects within the same treatment in the same figure on linear and log-linear scales. The profiles can be stratified by subject ID in blocks of 6 to reduce number of curves per plot.

Mean  $\pm$  SD PD data-time profiles for actual measurement and change from baseline results profiles for Parts 1a and 1b will be presented combining the curves for both IV and SC treatments within the same figure, on linear and log-linear scales.

For Part 2 PD data-time profiles for actual measurement and change from baseline results for all subjects vs dose day of treatment will be presented combined for all subjects within the same dose level. For the subjects requiring dose escalation the individual plots will be produced taking into account the day of the dose escalation.

### 10.3.3 Summary of PD concentrations and parameters in plasma

The PD results for Part 1a will be summarized by the treatment IV or SC administration of MarzAA.

**Statistical Analysis Plan**

Catalyst Biosciences, Inc. Protocol # MAA-201

Version 2.0

Syneos Health #1009647

For Part 2 the summary of PD results will be based on actual dose administered and will be presented relative to the start of dosing for the 1st dose level or day of dose escalation for all subsequent dose levels. The history of dose escalation i.e. the day of bleeding which required dose escalation will be taken into account for the summaries.

PD parameters and results will be summarized by treatment and time point using the following descriptive statistics:

Variable	Summarized with:
PD data at each nominal time point	n, number and % BLQ, arithmetic mean, SD, coefficient of variance (CV) %, minimum, median and maximum
AUE, Emax, CFB max , TA_AUE	n, arithmetic mean, SD, CV%, minimum, median, maximum, geometric mean and geometric CV%
TE max (actual time)	n, minimum, Q1, median, Q3 and maximum

Note: CV% = SD/mean in %.

%BLQ = 100 \* (total number of subjects who have BLQ values/total number of subjects within each treatment at each time point)

Mean concentrations will not be presented if 50% or more of the actual values for PD population at any one time point in the terminal phase are BLQ or missing.

Samples taken outside the allowed time windows may be excluded from summarization. This will be determined prior to database lock.

The following conventions will be used for the presentation of the descriptive statistics of PD results and parameters:

**PD Reporting Precision**

Statistics	Degree of Precision
Minimum, Maximum; Q1 (25%) and Q3 (75%)	3 significant digits or as needed based on actual measured values (for example PD concentrations)
Mean (arithmetic and geometric), Median	4 significant digits or as needed based on actual measured values (for example PD concentrations)
Standard deviation	5 significant digits or as needed based on actual measured values (for example PD concentrations)

**Statistical Analysis Plan**

Catalyst Biosciences, Inc. Protocol # MAA-201

Version 2.0

Syneos Health #1009647

CV% and Geometric CV%	1 decimal point or as needed based on actual measured values (for example PD concentrations)
-----------------------	--

Additionally, the following inferential analyses will be performed as described below in Sections [10.4](#) and [10.5](#) of the SAP:

**10.4 COMPARISON OF PD DATA TO BASELINE**

PD data at different time points in Part 2 of the study will be compared to baseline values using a repeated measures ANOVA model in the SAS Proc Mixed procedure including log e transformed PD actual measured data as dependent variable and visit as independent variable. The model will be conducted on the data including baseline and post-baseline visits (Days 7, 14, 21, 28 and 50). If data allow the same analysis may be repeated separately for dose levels 2 (60 µg/mL), 3 (90 µg/mL) and 4(120 µg/mL) using time relative to dose escalation day. The baseline will be considered as pre-dose value before the first dose at the 1st dose level.

The comparison will be performed for the dose level with at least 6 subjects of PD data available. Pair-wise comparisons will be made between PD values on Day 7 vs reference at baseline, Day 14 vs baseline and so on.

95% CIs for the geometric mean ratios (GMRs) will be obtained from the mixed-effects model. The formula for the calculation of the estimated ratio between the test and reference and the (1-2\*α)\*100 % CI of the ratio is given below.

Difference = Estimate of difference between test and reference LSMs

- Ratio =  $100 \times e^{\text{Difference}}$
- (1-2\*α)\*100% CIs for the Ratio:
  - Lower =  $100 \times e^{(\text{Lower Bound } (1-2*\alpha) \% \text{ CIs for the Difference})}$
  - Upper =  $100 \times e^{(\text{Upper Bound } (1-2*\alpha) \% \text{ CIs for the Difference})}$

The post-baseline visit where it shows statistically significant difference with baseline (p < 0.05) will be considered to represent the drug effect on PD results. Kenward-Rogers procedure will be used to resolve the issue of the small sample size. The confidence interval of the difference between each post- baseline visit vs. baseline visit will be also be presented conclude the significance of the difference.

The PD results with statistically significant difference with baseline will be considered for biomarkers of clinical outcome and will be advanced to further comparisons.

The comparison of PD values to baseline will also be explored graphically:

Statistical Analysis Plan

Catalyst Biosciences, Inc. Protocol # MAA-201

Version 2.0

Syneos Health #1009647

Box and whiskers plots of PD actual measured data with Days on X axis. Multiple days including baseline will be presented on the same plot.

## 10.5 EVALUATION OF THE RELATIONSHIP BETWEEN BLEEDING EVENTS AND PD DATA.

Each PD actual measured data in Part 2 will be grouped into bleeding and non-bleeding groups depending on if the subject at each PD visit is experiencing bleeding across all dose levels. The following ANOVA models will be conducted:

- log(e) transformed PD actual measured values as dependent variable and bleeding group based on PD actual measured data as independent variable
- change from baseline PD actual measured values as dependent variable and bleeding group based on PD actual measured data as independent variable

PD parameter data will also be grouped into bleeding and non-bleeding groups depending on if the subject is experiencing bleeding during the period for each dose level. The following ANCOVA model will be conducted:

- PD parameter ( $E_{\max/\min}$ ,  $CFB_{\max/\min}$ ,  $TA\_AUE$  and  $TA-AUE_{CFB}$ ) values as dependent variable, bleeding group based on PD parameter data as independent variable and baseline at each dose level of each subject will be used as covariate. The same model will be used separately for each dose level. Note that log e transformation will be done when the appropriate PD parameters is used.

The model will only be performed for the bleeding/non-bleeding groups for each dose level with at least 6 observations available.

Patients with dose escalation may contribute more than one observation to this comparison. The same subject data will be used in both groups with PD data for dose levels with bleeding event and PD data for the escalated doses resulting in stopping of bleeding events.

Contrasts for bleeding and non-bleeding groups will be evaluated. Multiple models may be explored and the model meeting the convergence criteria will be presented with the effects of all used covariates included in the table.

The results with statistically significant difference between groups ( $p < 0.05$ ) will be considered for biomarkers of clinical outcome. Kenward-Rogers method will be used to allow for robust convergence. Due to small sample size, the findings of the study will be considered exploratory and will require additional validation.

Graphic presentation for the comparison analysis will include box and scatter plots for the relevant PD concentration and parameter data for the two categories based on bleeding events.

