Dose interruption and surgery: Daily SC study injections will be interrupted, as needed, if there is a need for a surgical procedure; an event requiring extended (>48 hours) hospitalization; a thrombotic event; clinical evidence of inhibitor formation; or laboratory results suggesting an antibody may be developing.

Measurements:

MarZAA antigen and activity levels, as well as coagulation parameters, will be measured during Part 2 of the study at Day 1 (At pre-dose and Hour 7 post-dose, Day 3 (Pre-dose), Day 5 (Pre-dose), Day 7 (Pre-dose and Post-dose Hour 7).

MAA-201 VERSION 2.0

If no spontaneous bleeding occurs at the first dose level in part 2 of the study, trough antigen and activity, as well as coagulation parameters, will be measured on days 14, 21, 28, and 50 after starting their dosing regimen.

If spontaneous bleeding occurs after the fifth daily dose at any dose level, MarzAA antigen and activity levels will be measured within 6 hours of the spontaneous bleed (if feasible). Specimens for coagulation and immunogenicity testing will also be drawn.

Once it is determined to escalate to the next dose level, a pre-dose and Hour 7 post-dose specimen, will be drawn for PK, coagulation, and thrombogenicity markers on Day 7 *after* the dose has been escalated to estimate the *new* trough and peak concentrations (PCs) and PD. MarzAA antigen and activity levels, as well as coagulation parameters, will then be measured (pre-dose) at Day 14, 21, 28, and 50 after dose escalation.

Immunogenicity assays: Specimens for immunogenicity testing (antibody to MarzAA, neutralizing activity, cross reactivity) will be drawn at screening, Part 1a pre-dose, Part 1b pre-dose, and during part 2 pre-dose on Day 1, 7, 14, 21, 28, and 42, and then every two weeks until end of study.

Number of planned subjects: 12

Trial population:

Inclusion criteria:

1. Confirmed diagnosis of severe congenital hemophilia A or B with an inhibitor.
2. History of frequent spontaneous bleeding episodes (historical annualized bleeding rate [ABR] of ≥ 12).
3. Male, age 18 or older.
4. Agreement to use highly effective birth control throughout the study.
5. Affirmation of informed consent with signature confirmation before any trial-related activities. (Trial related activities are any procedure that would not have been performed during normal clinical management of the subject).
6. Stated willingness to comply with all study procedures and availability for the duration of the study.

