9.4.9 Exploratory Analyses

The following will be documented:

- Biomarker(s) such as antigen levels, activity levels, or global thrombosis assay evaluation that can be used to predict or correlate with a subject's lack of spontaneous bleeding.
- Biomarker(s) such as D-dimer, F1+2, or a functional assay of the FVIIa activity that will identify or predict clinical thrombogenicity with the daily SC administration of MarzAA.
- Biomarker(s) such as D-dimer, F1+2, or a functional assay of the FVIIa activity that will identify or predict clinical thrombogenicity of daily SC administration of MarzAA when use of rescue medication is required.
- PRO measures: EQ-5D, VAS; Haem-A-QoL; Hemophilia Activities List (HAL)

MAA-201 VERSION 2.0

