**Version 2.0**

**Syneos Health #1009647**

### **4.3 EXPLORATORY ENDPOINTS**

- Identification of biomarker(s) such as antigen levels, activity levels, or global thrombosis assay evaluation that can be used to predict or correlate with a subject's lack of spontaneous bleeding.
- Identification of biomarker(s) such as D-dimer, F1+2, or a functional assay of the FVIIa activity that will identify or predict clinical thrombogenicity with the daily SC administration of MarZAA.
- Identification of biomarker(s) such as D-dimer, F1+2, or a functional assay of the FVIIa activity that will identify or predict clinical thrombogenicity of daily SC administration of MarZAA when use of rescue medication is required.
- Patient-reported outcome (PRO) measures: European Quality of Life-5 Dimensions (EQ-5D), Visual analogue scale (VAS); Hemophilia A quality of life questionnaire (Haem-A-QoL); Hemophilia Activities List (HAL)

Statistical Analysis Plan

Catalyst Biosciences, Inc. Protocol # MAA-201

Version 2.0

Syneos Health #1009647

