### 9.1 PK SAMPLING SCHEDULE

PK sampling schedule will be specific to each part and dose administration. The PK data will be measured as MarzAA antigen concentration and activity levels. Additional PK data will include FVII, FVIIa activity.

Part 1a - single IV dose of 18 µg/kg MarzAA. PK sampling - predose, and post-dose at 5 and 30 minutes and Hour 1, 3, 6, 9, 12, and 24.

Part 1 b - single SC dose of 30 µg/kg MarzAA. PK sampling - pre-dose and Hour 3, 5, 7, 9, 12, 24, 30, and 48 post-dose.

Part 2 - daily SC dosing with variable dose to be determined.

PK sampling - Day 1 (Pre-dose and Post-dose Hour 7), Day 3 (Pre-dose), Day 5 (Pre-dose), Day 7 (Pre-dose). In the absence of spontaneous bleeding for the first dose level in Part 2 of the study, trough antigen and activity will be measured on days 14, 21, 28, and 50.

In case of spontaneous bleeding the PK samples will be taken within 6 hours of the spontaneous bleed and a pre- and 7 hours post-dose on Day 7, 14, 21, 28, and 50 after dose escalation.

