### 10.1 PD SAMPLING SCHEDULE

PD analysis includes following assessments

Coagulation assays	Thrombogenicity biomarkers
PT, aPTT, fibrinogen, and TGT	D-dimer, F1+2, and thrombin-antithrombin complexes (TAT)

PD sampling schedule will be specific to each part and dose administration.

Part 1a - single IV dose of 18 µg/kg MarzAA. PD sampling - predose, and post-dose at 5 and 30 minutes and Hour 1, 3, 6, 9, 12, and 24.

Part 1 b - single SC dose of 30 µg/kg MarzAA. PD sampling - pre-dose and Hour 3, 5, 7, 9, 12, 24, 30, and 48 post-dose.

Part 2 - daily SC dosing with variable dose to be determined.

PD sampling and assessments - Day 1 (Pre-dose and Post-dose Hour 7), Day 3 (Pre-dose), Day 5 (Pre-dose), Day 7 (Pre-dose). In the absence of spontaneous bleeding for the first dose level in Part 2 of the study, trough antigen and activity will be measured on days 14, 21, 28, and 50.

In case of spontaneous bleeding the PD samples will be taken within 6 hours of the spontaneous bleed and a pre- and 7 hours post-dose on Day 7, 14, 21, 28, and 50 after dose escalation.

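### The exploratory endpoint names antigen and activity levels as candidate markers of freedom from spontaneous bleeding, but the only marker-versus-bleeding analysis (SAP 10.5) is written for PD data that omit both and leaves bleeding undefined

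*SAP*

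**What the plan says.** SAP 4.3 sets as its first exploratory endpoint "Identification of biomarker(s) such as antigen levels, activity levels, or global thrombosis assay evaluation that can be used to predict or correlate with" freedom from spontaneous bleeding. The same aim appears in protocol 3.3, 9.1 and 9.4.9. Protocol 9.4.9 gives no method; its lead-in is only "The following will be documented".

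SAP 10.5 relates markers to bleeding. It begins: "Each PD actual measured data in Part 2 will be grouped into bleeding and non-bleeding groups". Two ANOVA models use visit-level PD values, grouped by whether the subject is bleeding at the visit. One ANCOVA uses derived PD parameters, grouped by whether the subject bled during the dose-level period.

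The PD assay table in SAP 10.1 has a coagulation column, "PT, aPTT, fibrinogen, and TGT", and a thrombogenicity column with D-dimer, F1+2 and TAT. SAP 9.1 defines the PK data as MarzAA "antigen concentration and activity levels. Additional PK data will include FVII, FVIIa activity".

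The data for the missing comparison are collected. For a spontaneous bleed after the fifth daily dose, the protocol synopsis says that MarzAA "antigen and activity levels will be measured within 6 hours of the spontaneous bleed (if feasible"). SAP 9.1 also schedules pre-dose samples through Part 2.

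**The concern.** The trial asks whether drug level goes with protection from spontaneous bleeding, measures drug level, and then plans no comparison that could answer the question. A programmer who follows 10.1 and 10.5 would run PT, aPTT, fibrinogen, TGT and the thrombogenicity markers against bleeding and would leave out antigen and activity. Any later comparison of drug level with bleeding would be post hoc.

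The outcome has the same weakness. The endpoint concerns what may "correlate with a subject's lack of spontaneous bleeding", whereas 10.5 speaks of bleeding without saying which kind. Spontaneous bleeds are the ones that matter to the design: they trigger escalation (protocol 6.1.2.1), define each subject's optimal dose (protocol 3.2) and decide completion at the first three dose levels (protocol 4.2). The grouping rule should not be left to be settled at the programming stage.

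**Working it through.** No figure in the plan is in question and no formula applies. The check follows the endpoint through every SAP section that could serve it.

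| SAP section | What it does with antigen and activity | Compared by bleeding status? |
|---|---|---|
| 8.2.1 | Not used; analyses bleeds, bleeding intervals and bleeding days | No marker involved |
| 8.2.3 | One entry in the coagulation list; actual values and change from baseline | No |
| 8.3 | Not used; patient-reported outcomes only | No |
| 9.3 | Listings, plots and summaries by dose, allowing for the escalation day | No |
| 9.4 | Attainment of steady state | No |
| 9.5 | Dose proportionality | No |
| 10.1 | Absent from the assay table | Not applicable |
| 10.4 | PD values against baseline | No |
| 10.5 | PD values and PD parameters only | Yes, but antigen and activity are not in the PD table |
| 9.6, 10.7, 14 | Dropping this part of the endpoint is not declared as a change | Not applicable |

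Coverage of the endpoint's named markers:

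- Antigen levels: 0 planned comparisons with bleeding.
- Activity levels: 0 planned comparisons with bleeding.
- Global thrombosis assay: covered only if TGT or the thrombogenicity markers are taken to be that assay.

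Models in 10.5 whose bleeding group is stated to be spontaneous bleeds: 0 of 3 (two ANOVA, one ANCOVA).

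Data already available: after Day 1, a subject who stays at 30 µg/kg has pre-dose samples on Days 3, 5, 7, 14, 21, 28 and 50, which is 7 values. After an escalation the pre-dose days are 7, 14, 21, 28 and 50, which is 5 values. The spacing limits any repair. The nominal gap from Day 28 to Day 50 is 50 − 28 = 22 days, so the last level before a late bleed may be about three weeks old.

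Size limits: 10.5 runs its bleeding/non-bleeding comparison at a dose level only with at least 6 observations, and does not say whether this is in total or per group. Suppose it is per group, with one parameter value per subject and 12 subjects. Then 6 + 6 = 12, and the ANCOVA at 30 µg/kg could run only on an exact six-to-six split. That is a reason to prespecify a descriptive comparison alongside any model.

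**The case against.** Several points on the other side are sound.

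- The SAP is inconsistent about these markers. The text below the table in 10.1 mentions trough antigen and activity, and SAP 4.2 and 8.2.3 list antigen and activity with the coagulation parameters. One could argue that they belong in 10.5. But the assay table omits them, 9.1 classes them as PK, and 8.2.3 plans only summaries. The inconsistency makes clarification more necessary.
- A reader might infer that 10.5 counts any bleed, so that a traumatic bleed places a protected subject in the bleeding group. The text does not say this. It leaves the word undefined, and its reference to escalated doses that stop bleeding leans towards spontaneous bleeds, since only those trigger escalation. The pooled definition in 8.2.1 is for breakthrough bleeds, a term 10.5 does not use. What stands is that the outcome is not secured.
- A reader might infer that drug level is never connected to bleeding at all. That goes too far. PK summaries and individual plots take account of the escalation day, which follows a spontaneous bleed. These displays are useful, but they do not compare levels with and without bleeding.
- A reader might infer that this is the trial's main route to a dose or a target trough. The documents do not say so. Dose information comes from within-subject escalation, the number escalating, and the bleeding rate at the final dose.
- The marker list is illustrative, the endpoint is exploratory, and 10.5 says its findings need validation. This limits the weight of the point, but antigen and activity are still the first examples given.

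**Conclusion.** The gap is real and limited in scope. Two of the three markers named in the endpoint have no planned comparison with bleeding, and none of the three models in 10.5 fixes the outcome as spontaneous bleeding. SAP 5.7 refers to PK/PD analyses, but none is specified.

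This rests on two readings: that the endpoint's antigen and activity levels are those of MarzAA, which 9.1 supports, and that the assay table in 10.1 determines what 10.5 treats as PD data. If the authors meant 10.5 to include antigen and activity, the defect is one of wording, and the remedy is nearly the same.

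No primary or secondary result changes. The point merits action because the trial sets this question itself, already holds the data, and can answer it with a small edit to an existing analysis.

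**What to change.** In SAP 10.5:

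1. Add MarzAA antigen and activity to the markers analysed. Check FVIIa activity too: a functional assay of it is named in the other two biomarker endpoints, but SAP 9.1 also classes it as PK.
2. Define the bleeding group as spontaneous bleeds and show traumatic bleeds separately.
3. Use the last pre-dose level before the bleed as the main value, and say what is done when no pre-dose level at the current dose precedes it. Show the sample within 6 hours of the bleed separately, because bypass treatment may already have been given (protocol 8.2.6.1).
4. Account for repeated observations, for example with subject as a random effect.
5. Prespecify a descriptive comparison of levels with and without spontaneous bleeding as the fallback if the model does not converge.

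Dose level should not be a required covariate. It largely determines drug level, so adjusting for it would remove much of the contrast being sought.

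The cost is SAP wording and a small amount of extra exploratory analysis, with no new samples or visits. Two limits remain and should be stated with the results: precision is low with 12 subjects, and dose is confounded with bleeding tendency because those who bleed are the ones escalated.

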6.1.2.1 Guidelines for Dose Escalation

An escalation to the next dose level is required if a spontaneous bleeding event occurs after the fifth daily dose on a dose level. A dose escalation will not occur if the subject is on the maximum dose level of 120 µg/kg. A spontaneous bleeding episode is defined as one that is precipitated by normal activities of daily living (ADL). Subjects will use their current bypass regimen for any spontaneous or traumatic bleed that occurs while on study drug.

Three dose escalations are allowed during Part 2: 60, 90, and 120 µg/kg (maximum dose).

Safety parameters and PK/PD assessments at each dose level will be monitored to ensure that dose escalation to a higher dose level is appropriate.

The spontaneous bleeding episode must be reported to the clinical team immediately and determination of a dose escalation will be made on review of available clinical information related to the spontaneous bleeding episode and may require subsequent treatment and laboratory data, including available results from the PK/PD/safety assessments.

A decision to proceed with dose escalation will be made by the principal investigator in agreement with personnel who have Sponsor, or designee, medical oversight responsibility.

If there is disagreement amongst any of those individuals, the decision will be reviewed on an urgent basis by an independent Medical Consultant for Safety Oversight.

MAA-201 VERSION 2.0

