**Statistical Analysis Plan**

Catalyst Biosciences, Inc. Protocol # MAA-201

Version 2.0

Syneos Health #1009647

AUE and AUE CFB	Area under curve effect vs time profile for actual measurements and change from baseline
TA_AUE and TA_AUE CFB	Time adjusted area under curve effect vs time profile for actual measurements and change from baseline

The PD parameters will be estimated as follows:

The apparent  $E_{max}$  and the corresponding  $CFB_{max}$  and  $T_{max}$  will be read directly from the PD value-time plot (observed data, not predicted data by the program);

AUEs will be calculated using the linear-log trapezoidal rule both for measured data and change from baseline;

TA\_AUE will be estimated as AUE divided by the time elapsed from assessment.

The parameters will be derived for the complete duration of treatment starting from the dose in Parts 1a and 1 b and from the first injection for each dose level in Part 2 of the study.

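### The dose-level PD comparison in SAP 10.5 uses whole-period extremes, although at 30, 60 and 90 µg/kg a qualifying spontaneous bleed cuts sampling short

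*SAP*

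**What the plan says.** SAP 10.5 has two sets of models. The second takes PD parameters (Emax/min, CFBmax/min, TA_AUE and TA_AUE_CFB), "grouped into bleeding and non-bleeding groups depending on if the subject is experiencing bleeding during the period for each dose level". On adjustment it says only that "baseline at each dose level of each subject will be used as covariate", and "The same model will be used separately for each dose level". A data threshold applies: "The model will only be performed for the bleeding/non-bleeding groups for each dose level with at least 6 observations available". Differences at p<0.05 make a marker a candidate biomarker of clinical outcome. The same paragraph calls the findings exploratory, because of the small sample, and in need of validation.

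SAP 10.2 sets the window: "The parameters will be derived for the complete duration of treatment starting from the dose in Parts 1a and 1 b", and in Part 2 "from the first injection for each dose level in Part 2 of the study". Emax/min and CFBmax/min are read off as observed extremes in that window. TA_AUE is divided by elapsed time.

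Protocol 6.1.2.1 decides when a level stops: "An escalation to the next dose level is required if a spontaneous bleeding event occurs after the fifth daily dose on a dose level", except at the 120 µg/kg maximum. Protocol 8.2.6 then resets the day count. Under Protocol 4.2, a subject on the first three levels must go 50 days without a spontaneous bleed. The analysis serves the SAP 4.3 endpoint of finding biomarkers that "can be used to predict or correlate with a subject's lack of spontaneous bleeding".

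**The concern.** At the three lower levels, the event that places a subject in the bleeding group can also end that subject's sampling. The expected maximum of a set of measurements grows with their number, and the expected minimum falls. A comparison of whole-period extremes therefore mixes two things: whether the marker relates to bleeding, and how long the subject was observed. The model has no term for duration or number of samples, and no common window or landmark is set.

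At stake is which of the seven markers in SAP 10.1 (PT, aPTT, fibrinogen, TGT, D-dimer, F1+2, TAT) are carried forward. With pre-bleed samples only, the artefact makes bleeders look like weaker PD responders, which is the pattern the endpoint is looking for.

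**Working it through.** The documents give no figure for this comparison, so there is nothing to reproduce.

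**Post-baseline samples for a non-bleeder.** At 30 µg/kg (SAP 10.1): Day 1 hour 7, then Days 3, 5, 7, 14, 21, 28 and 50, so 8. At escalated levels, SAP 10.1 gives pre-dose and hour 7 on Days 7, 14, 21, 28 and 50, so 10. Protocol 4.1 gives hour 7 on Day 7 only, so 6.

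**Samples for a bleeder.** Assume a constant 12 bleeds/year (the null rate) from Day 5, with the bleed before Day 50. The daily rate is r = 12/365.25 = 0.03285, and the chance of staying bleed-free over the 45 days is q = exp(-45r) = 0.228. The chance that a bleeder reaches day d is [exp(-r(d-5)) - q]/(1 - q): 0.918 for Day 7, 0.669 for Day 14, 0.470 for Day 21, 0.313 for Day 28.
- 30 µg/kg: 3 + 0.918 + 0.669 + 0.470 + 0.313 = 5.4, against 8.
- Escalated, SAP schedule: 2 × (0.918 + 0.669 + 0.470 + 0.313) = 4.7, against 10.
- Escalated, Protocol 4.1 schedule: 2 × 0.918 + 0.669 + 0.470 + 0.313 = 3.3, against 6.

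A bleed on Day 10 leaves 4 of 8, 2 of 10 or 2 of 6.

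**Why the count matters.** The expected maximum of n independent standard normal values is 0.56 for n = 2, 1.03 for 4, 1.42 for 8 and 1.54 for 10. Within-subject correlation shrinks these gaps but does not remove them.

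**Size with no true link.** Measurement = subject effect (variance ρ) + error (variance 1 - ρ), total SD 1, with ρ assumed 0.3-0.5. Emax is regressed on group and baseline, two-sided 5%, 20,000 simulated trials per setting. CFBmax is Emax minus baseline, so with baseline in the model its group coefficient is the same. Bleeders with no sample at a level are left out. Drift means an assumed rise of 1 SD over 50 days.

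| Level | Bleed-time sample | Bleeders lower by (SD) | Rejects, 6 v 6 | Rejects, 3 v 3 | 6 v 6 with drift, ρ = 0.5 |
|---|---|---|---|---|---|
| 30 µg/kg | no | 0.17-0.21 | 6.3-7.1% | 5.4-5.6% | 16.6% |
| 30 µg/kg | yes | 0.10-0.12 | 5.6% | 5.2-5.3% | 10.3% |
| Escalated, SAP | no | 0.33-0.38 | 10.5-11.5% | 6.4-6.9% | 26.0% |
| Escalated, SAP | yes | 0.30-0.35 | 9.4-9.9% | 6.0-6.2% | 21.3% |
| Escalated, Protocol 4.1 | no | 0.25-0.30 | 8.3-8.8% | 5.8-6.1% | 19.3% |
| Escalated, Protocol 4.1 | yes | 0.19-0.23 | 6.8-6.9% | 5.1-5.6% | 13.2% |

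At 6 bleeds/year the lowest escalated value falls to 0.15 SD. For TA_AUE without drift the difference is about 0, with 4-6% rejections. With no truncation, as at 120 µg/kg, the Emax difference is 0.01 SD, with 4.4% rejections.

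**How likely is 6 v 6?** At 30 µg/kg with 12 subjects: 924 × 0.228⁶ × 0.772⁶ = 0.027. At 60 µg/kg all 12 must first escalate: 0.772¹² × 0.027 = 0.0012, about 0.1%.

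**With a common window.** Taking the extreme through Day 5 at 30 µg/kg, or Day 7 at escalated levels, gives a group difference of 0.00-0.01 SD and about 5% rejections, with or without the drift.

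**The case against.** The strongest reply is that the effect is small and sits in a secondary model for an exploratory endpoint. For a stable marker at 30 µg/kg, where half of the post-baseline samples fall by Day 7, the test stays near its nominal level. The SAP requires validation. SAP 10.4 first screens for change from baseline, and 10.5 also has a visit-level model that uses no extremes. All of this stands and limits the weight of the point. It does not remove the bias. The SAP justifies its caution by sample size, not unequal observation, and the 10.4 screen passes a marker that responds to the drug but is unrelated to bleeding.

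The sample within 6 hours of a bleed (SAP 10.1) does help, as the table shows. It is taken if feasible, and the Protocol's Day 0 list has coagulation assays but no thrombogenicity markers.

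Four stronger readings are tempting and not supported:
- That every bleed truncates the period. Traumatic bleeds, bleeds before the fifth dose and bleeds at 120 µg/kg do not. SAP 10.5 groups on bleeding without saying spontaneous, so some bleeders keep a full window.
- That the artefact always makes bleeders look weaker. Under Protocol 8.2.6.1 subjects treat the bleed and then call, so the Day 0 draw may follow bypassing treatment and could raise a bleeder's extreme.
- That the upper escalated-level rates are what to expect. They need a 6 v 6 split. If the six-observation rule is per group, the model will rarely run there; if it is per level, 3 v 3 is the more relevant case.
- That TA_AUE fails in the same way. It is already divided by time and is largely protected without drift.

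**Conclusion.** The point holds for Emax/min and CFBmax/min at 30, 60 and 90 µg/kg, where the bleed is spontaneous and follows the fifth daily dose. For a stable marker the bias is about 0.1-0.2 SD at 30 µg/kg and 0.15-0.4 SD at escalated levels, the lower ends counting the bleed-time sample. False positives are about 5-8% at 30 µg/kg. At escalated levels they are about 6-12% with 6 v 6 and 5-7% with 3 v 3. If the marker rises by 1 SD over 50 days, the 6 v 6 rates are about 17-26% without the bleed-time sample and 10-21% with it.

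The correlation, drift, constant bleed rate and group sizes are assumptions; the documents give no marker variability. The direction is not assured if post-treatment samples enter. The primary ABR analysis and the safety analyses are untouched. It is a biased stated rule, modest in most plausible settings and inexpensive to correct before results are seen.

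**What to change.** In the dose-level model of SAP 10.5, replace whole-period Emax/min and CFBmax/min by one of two time-matched comparisons:
- the last scheduled trough before the bleed, against the trough on the same dose-level day in subjects still bleed-free at that level; or
- the extreme over a fixed early window that all compared subjects complete: through Day 5 at 30 µg/kg and through Day 7 at escalated levels, with earlier bleeds listed.

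Exclude samples drawn after bypassing treatment. Keep TA_AUE and TA_AUE_CFB in the model. Report whole-period Emax/min and CFBmax/min descriptively, with days observed and number of samples. Do not cut non-bleeders at the bleeders' median bleed day, because earlier bleeders would still have fewer samples. The same edit should state which bleeds define the bleeding group and whether the six-observation minimum is per group or per level.

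The cost is SAP wording and modest programming, with no new data. The downside is that later samples from non-bleeders go unused in this model.
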